This is a prospective investigator initiated single-center open-label, non-placebo controlled pilot study. All patients meeting the inclusion criteria would be screened for eligibility and after informed consent, randomization would be performed to either the Cilostazol treatment (drug group) or the non-Cilostazol treatment (control group) groups, stratified for endovascular or open interventions, using a closed envelope randomization technique. Eligible patients would be consented prior to surgery or within 48 hours of index procedure. Patients on Cilostazol prior to surgery would still be eligible and medication discontinued if randomized to control group. Cilostazol will be provided to patients randomized to the treatment arm free of charge for three months. . If you are randomized to the treatment arm (receiving Cilostazol) we will provide you with Cilostazol 100 mg, twice a day, free of charge for a period of three months. Patients who have renal impairment (problems with their kidneys) will be given 50 mg, twice a day instead of 100 mg, twice a day. Cilostazol has a half- life of 13 hours, therefore a washout period will not be necessary. Concurrent medication use based on comorbidities including diabetic, anti-hypertensive medications, lipid lowering agents would be prescribed based on standard practice and not dependent on study group or enrollment in the study. Also concurrent use of single or dual antiplatelet therapy (aspirin with or without ADP receptor blocker or similar medication) would be used at discretion of treating physician. Patients who need to be on anticoagulation, with warfarin or other oral anticoagulants, for high risk revascularization or other comorbidities, would have single antiplatelet agent (as above) only for secondary prevention of thrombotic events. Cilostazol use in either group would not lead to a change in their antiplatelet/anticoagulation regimen.

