Pre-operative demographic, medication use and co-morbidity data and operative data would be retrieved from EMR. Patient follow up would be based on our current standard protocol which includes duplex of the graft or intervened artery at 4-6 weeks and 3-6 months. Cilostazol will be provided to patients free of charge for three months. Restenosis is defined as stenosis>50% based on our current vascular laboratory criteria or based on arteriogram imaging if performed at discretion of treating physician. Clinical examination and medication use and other secondary and adverse outcomes would be evaluated and QOL questionnaires administered at above time points. Quality-of-life (QOL) questionnaires (EQ-5D and EACH Qc) will be administered at enrollment and each follow up visit.

Purpose

The primary purpose of this pilot study is to collect QOL data on patients undergoing peripheral revascularization in order to determine the sample size required for adequate powered trial of Cilostazol versus usual care without Cilostazol and its effect on QOL. Thirty patients, fifteen in each arm, will be recruited into the pilot study in order to obtain sufficient data needed to estimate the variance and within-subject correlation of the outcome measures.

Benefits/Risks

Benefits include: possible improvement in quality of life for patients suffering from claudication after revascularization, improvement in graft patency and decreased restenosis and potential amputation. Risks include possible allergic reaction to the drug.

Inclusion

1. Patients should be older than 35 years of age
2. Patients treated for atherosclerotic PAD
3. Able to provide informed consent
4. Lower extremity open or endovascular revascularization, including bypass (autogenous or prosthetic), angioplasty and/or stenting, with or without concomitant aorto-iliac intervention.

Exclusion

1. Known congestive heart failure Class III/IV, systolic, acute or chronic
2. Allergic reaction to phosphodiesterase inhibitors
3. Intracranial bleeding within 3 months or active bleeding peptic ulcer disease
4. Traumatic vascular injuries requiring revascularization

5. Pregnant or breast feeding women, or plan to get pregnant over the study period (for five years after enrollment)
6. Planned ipsilateral major amputation within 30 days of index procedure
7. Moderate to severe hepatic impairment

Analysis

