Data will be collected and stored on a password protected secure server which only study team members can access. QOL instruments (EQ-5D and EACH Qc) will be scored from the baseline, 4-6 week and 3 month visits. Cross-sectional and change scores will be calculated to estimate effect size and variance of QOL outcomes measures. These data will be used to assess potential efficacy and to project sample size requirements for a future trial. Treatment arm differences in early (4-6 week) and late (3 month) month changes in QOL scores will be tested using two-group t-tests.

Follow-up graft patency will be assessed as a secondary outcome and will be measured early (within 14 day of intervention) and late (six weeks and three months) using duplex ultrasound.

Treatment arm differences time to patency failure will be compared using Kaplan-Meier survival curves and log-rank tests. Information on the following tertiary outcomes will also be ascertained at six weeks and three months follow-up: (1) amputation, (2) death due to any cause, (3) clinical symptoms of claudication or rest pain (critical limb ischemia), and (4) stroke. Statistical comparison for differences between groups will not be performed for tertiary outcomes due to small sample size and power.

Confidentiality and Privacy

Confidentiality will be protected by collecting only information needed to assess study outcomes, minimizing to the fullest extent possible the collection of any information that could directly identify subjects, and maintaining all study information in a secure manner. To help ensure subject privacy and confidentiality, only a unique study identifier will appear on the data collection form. Any collected patient identifying information corresponding to the unique study identifier will be maintained on a separate master log. The master log will be kept secure, with access limited to designated study personnel. Following data collection subject identifying information will be destroyed at the earliest opportunity, consistent with data validation and study design, producing an anonymous analytical data set. Data access will be limited to study staff. Data and records will be kept locked and secured, with any computer data password protected. No reference to any individual participant will appear in reports, presentations, or publications that may arise from the study.

Data and Safety Monitoring

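### The t-tests on QOL change fix the baseline coefficient at 1 and omit the open/endovascular stratum; a model adjusting for both uses data already collected and is usually more precise

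*Combined protocol and SAP*

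**What the plan says.** The Analysis section gives the whole of the QOL comparison: "Treatment arm differences in early (4-6 week) and late (3 month) month changes in QOL scores will be tested using two-group t-tests". It names no covariate. It also says "Cross-sectional and change scores will be calculated to estimate effect size and variance of QOL outcomes measures", and gives the use of the results: "These data will be used to assess potential efficacy and to project sample size requirements for a future trial".

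Three statements elsewhere bear on this:

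- **Randomisation (Methods):** "stratified for endovascular or open interventions, using a closed envelope randomization technique".
- **Baseline and its timing (Methods):** "Quality-of-life (QOL) questionnaires (EQ-5D and EACH Qc) will be administered at enrollment and each follow up visit", and "Eligible patients would be consented prior to surgery or within 48 hours of index procedure".
- **Sample size (Purpose):** "Thirty patients, fifteen in each arm, will be recruited into the pilot study", the reason being "in order to obtain sufficient data needed to estimate the variance and within-subject correlation of the outcome measures".

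Nothing in the document adjusts the QOL comparison for baseline score or for type of procedure.

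**The concern.** A t-test on change scores is a regression of follow-up on arm in which the baseline coefficient is set to 1 instead of estimated. It loses precision to the extent that the true slope differs from 1. The slope is ρ × (follow-up SD / baseline SD), where ρ is the correlation between the two scores. Nothing in the plan supports a slope near 1. Baseline is taken at enrolment, either before surgery or within 48 hours of the procedure, and follow-up comes weeks to months after revascularisation. The within-subject correlation is itself something the pilot is meant to estimate.

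Leaving out the stratum costs further precision only if open and endovascular patients differ in how much their QOL changes. A stratum difference that is the same at both visits cancels in the change score.

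At stake is the width of the interval for the arm difference, which will be used to judge potential efficacy and to plan a later trial. With 15 per arm that interval is already wide.

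**Working it through.** **Inputs from the document.** 30 patients, 15 per arm; t-test on change; stratification by procedure; QOL at enrolment and at each visit. The document gives no alpha, target effect, SD, correlation or power for QOL, so the figure of 30 can be checked only as 2 × 15.

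**Inputs assumed.** ρ = 0.3, 0.5, 0.7, 0.9; k = follow-up SD / baseline SD = 0.8, 1, 1.25, 1.4; several stratum effects; strata of 16 and 14 patients; two-sided 5% level; an effect of 0.8 follow-up SD for power.

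**Step 1: large-sample variance.** In units of baseline variance, the change score has variance 1 + k² − 2ρk, and follow-up adjusted for baseline has k²(1 − ρ²). Since 1 + k² − 2ρk = (1 − ρk)² + k²(1 − ρ²), the ratio of change-score to adjusted variance is

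1 + (1 − ρk)² / [k²(1 − ρ²)].

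At k = 1 this is 2/(1 + ρ); for example, ρ = 0.5 gives 2/1.5 = 1.33. At k = 0.8 and ρ = 0.5 it is 1 + 0.36/0.48 = 1.75.

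| k | ρ = 0.3 | ρ = 0.5 | ρ = 0.7 | ρ = 0.9 |
|---|---|---|---|---|
| 0.8 | 1.99 | 1.75 | 1.59 | 1.64 |
| 1 | 1.54 | 1.33 | 1.18 | 1.05 |
| 1.25 | 1.27 | 1.12 | 1.02 | 1.05 |
| 1.4 | 1.19 | 1.06 | 1.00 | 1.18 |

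The ratio is never below 1. The adjusted model can lose only through estimating extra coefficients in a small sample, which Step 2 examines.

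**Step 2: 15 per arm, by simulation (20,000 trials per setting).** The t-test (28 df) is compared with a linear model on arm, baseline and stratum (26 df). The CI ratio is mean t-test width divided by mean adjusted width, so values above 1 favour adjustment. "Balanced" means arms balanced within strata; "not balanced" means 15/15 overall only.

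Equal SDs, no stratum effect:

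| ρ | CI ratio, balanced | CI ratio, not balanced | Power, t-test vs adjusted (balanced) |
|---|---|---|---|
| 0.3 | 1.21 | 1.19 | 43% vs 58% |
| 0.5 | 1.13 | 1.11 | 56% vs 66% |
| 0.7 | 1.06 | 1.04 | 78% vs 82% |
| 0.9 | 1.00 | 0.985 | both above 99% |

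Unequal SDs, ρ = 0.7, no stratum effect:

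| k | Slope ρk | CI ratio, balanced | CI ratio, not balanced |
|---|---|---|---|
| 0.8 | 0.56 | 1.23 | 1.21 |
| 1.25 | 0.875 | 0.99 | 0.97 |
| 1.4 | 0.98 | 0.98 | 0.96 |

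**Step 3: the stratum.** At ρ = 0.5, k = 1, balanced:

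| Open/endovascular difference | CI ratio | Power, t-test vs adjusted |
|---|---|---|
| 0.8 SD at both visits | 1.13 | 56% vs 66% |
| 0.4 SD at follow-up only | 1.15 | about 54% vs 66% |
| 0.8 SD at follow-up only | 1.22 | 50% vs 66% |

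The first row equals the result with no stratum effect, which confirms the cancellation. In the last row the t-test's type I error is 0.035, so it is conservative when arms are balanced within strata; it is 0.051 when they are not.

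**Step 4: the residual variance as a planning input.** On 26 df its 95% interval runs from 26/41.92 = 0.62 to 26/13.84 = 1.88 times the estimate.

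**Cross-check.** A separate simulation at k = 1, ρ = 0.5 and no stratum effect gave an adjusted-to-change variance ratio of 0.78. The adjusted analysis of 30 patients is then worth about 30/0.78 ≈ 38 patients analysed by t-test.

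**The case against.** The best case for leaving the plan alone has four parts.

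- **No error is present.** The t-test is valid, so this is a choice between two acceptable analyses. That stands, and it is why the point concerns precision only.
- **Sizing is mostly covered.** The pilot already plans to estimate visit variances and the within-subject correlation. Those give the baseline-adjusted variance directly, as follow-up variance × (1 − ρ²). This also stands. What the planned summaries do not give is a variance adjusted for stratum as well, and they do not narrow the pilot's own interval for the arm difference.
- **The gain is unknown and may be nil or negative.** This is true. At ρ = 0.7, k = 1.25, no stratum effect and arms not balanced within strata, the t-test has slightly more power, 83% against 81%. The Methods section mentions no blocking, so balance within strata is not assured. But the largest loss in the settings tried is an interval about 4% wider, while the t-test's interval is up to 23% wider in the settings tabulated.
- **The near-even stratum split is an assumption.** With 6 open cases among 30, the ratio of 1.22 for a 0.8 SD shift at follow-up only falls to 1.19 balanced, or 1.17 not balanced. The conclusion does not change.

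Power is a secondary yardstick, because the plan sets no target effect. The interval widths do not depend on one.

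**Conclusion.** The concern holds as a point of efficiency. The planned test is sound but discards information the trial already collects. For slopes well below 1 it widens the interval for the arm difference appreciably: by 13% at ρ = 0.5 with equal SDs, and by 22% if there is also a 0.8 SD open/endovascular difference at follow-up only. For slopes of about 0.9 to 1 with no stratum effect on change, adjustment gains nothing and can cost 1-4% in width. All these figures rest on assumed correlations, SD ratios, stratum effects and a near-even stratum split, since the document gives none of them. The change should be made, but the trial's validity does not depend on it. Confidence in the size of the gain is medium.

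**What to change.** In the Analysis section, replace the two-group t-tests with a linear model of the follow-up QOL score on treatment arm, baseline score and open/endovascular stratum, fitted at 4-6 weeks and at 3 months. Report the arm difference with its 95% confidence interval. Report the model's residual variance with its confidence interval, next to the planned variances and within-subject correlation, as an input for sizing a later trial that uses the same analysis.

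This changes wording only. Baseline QOL is already scheduled and the stratum is known at randomisation. The price is two degrees of freedom (26 instead of 28) and the slightly wider interval described above when the slope is near 1.

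### The patency log-rank test does not name the open/endovascular randomisation stratum; the likely cost is a slightly conservative test and a small loss of power, so the priority is minor

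*Combined protocol and SAP*

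**What the plan says.** In the Combined protocol and SAP, the Methods section describes randomisation as "stratified for endovascular or open interventions, using a closed envelope randomization technique". It states no block size or other restriction within strata.

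The Purpose section sets the size: "Thirty patients, fifteen in each arm, will be recruited into the pilot study". The reason given is to obtain "sufficient data needed to estimate the variance and within-subject correlation of the outcome measures". There is no power target, effect size or event count.

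On patency, the Analysis section states: "Follow-up graft patency will be assessed as a secondary outcome". It is to be assessed by duplex within 14 days, at six weeks and at three months, and the arms' times to patency failure "will be compared using Kaplan-Meier survival curves and log-rank tests". The section names no stratified log-rank test, no Cox model and no analysis within procedure. The stratification factor does not appear in it at all. No significance level or sidedness is stated, and no expected failure rates are given for either procedure.

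**The concern.** Procedure was judged important enough to stratify the randomisation, then left out of the patency comparison. Read in the usual way, an unqualified log-rank test puts bypass grafts and treated arteries into one risk set.

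When arms are balanced within strata, differences between the strata can no longer contribute to the difference between arms. The ordinary log-rank variance still counts them. If the two procedures fail at different rates, the variance is too large for the design, the test rejects too seldom under the null, and power is lost.

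Patency is the only outcome other than quality of life that the plan formally tests, and failures will be few. Information already built into the design should not be discarded without reason. Changing the quality-of-life comparison would leave this test as it is.

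**Working it through.** **Inputs from the documents.** N = 30, 15 per arm; strata open and endovascular; duplex within 14 days, at six weeks and at three months; log-rank test.

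**Inputs assumed because the documents give none.** Two-sided 5% level; the split between procedures; 3-month control-arm failure risks by procedure; hazard ratios; exponential failure times; no dropout. The sample size was not derived from a power calculation, so there is no figure of the plan's own to reproduce.

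**Step 1. Approximate level by hand.** Treat 3-month failure as a proportion, with equal strata, risks a and b, and mean p = (a + b)/2. The ordinary test uses a variance proportional to p(1 - p). With balance within strata, the true variance is proportional to [a(1 - a) + b(1 - b)]/2. If R is true over assumed variance, the actual level is P(|Z| > 1.96/√R).

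| Risks | Assumed | True | R | 1.96/√R | Level |
|---|---|---|---|---|---|
| 20/20% | 0.160 | 0.160 | 1.000 | 1.960 | 5.0% |
| 20/40% | 0.210 | 0.200 | 0.952 | 2.008 | 4.5% |
| 10/40% | 0.1875 | 0.165 | 0.880 | 2.089 | 3.7% |
| 10/50% | 0.210 | 0.170 | 0.810 | 2.178 | 2.9% |
| 15/60% | 0.2344 | 0.1838 | 0.784 | 2.214 | 2.7% |
| 10/60% | 0.2275 | 0.165 | 0.725 | 2.301 | 2.1% |

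**Step 2. Simulation with balance within strata.** 9,000 trials per scenario, 50:50 strata, failures dated at visits. The Monte Carlo standard error is about 0.2 points for level and up to 0.5 for power. Entries are ordinary v stratified.

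| Risks | Level | Power, HR 0.5 | Power, HR 0.25 |
|---|---|---|---|
| 20/20% | 5.2% v 5.0% | 9.6% v 9.5% | 17.8% v 17.9% |
| 30/10% | 4.5% v 5.4% | 8.9% v 10.1% | 17.8% v 19.3% |
| 40/10% | 4.0% v 5.2% | 10.3% v 12.3% | 23.7% v 26.7% |
| 60/10% | 2.4% v 5.0% | 10.5% v 15.5% | 32.1% v 39.5% |

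At a more extreme 80/10% the level is 1.0% v 5.3%.

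A further set used strata of 16/14 or 20/10 and a hazard ratio of 0.3. At 20% v 40% the level was 4.6-4.7% against 5.0-5.4%, and stratifying gained about 1 power point. At 10-15% v 50-60% the level was 2.5-2.9% against 4.7-5.4%; power was 15-27% against 20-33%, a gain of 4 to 6 points. A repeat run gave levels of 2.6-3.0% and gains of 4 to 7 points. These agree with Step 1.

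**Step 3. Simulation without balance within strata.** With simple randomisation within strata, the ordinary test's level was 4.9% at 40/10% and 5.1% at 60/10%. Power at a hazard ratio of 0.25 was 23.1% v 24.1% and 31.4% v 36.2%. At a hazard ratio of 0.3 the gain was about 1 to 4 points at very unequal risks, and nil or a trivial loss otherwise.

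**Step 4. Scale.** Under the null at 60/10%, expected failures are 15 × 0.60 + 15 × 0.10 = 10.5; at 40/10%, 15 × 0.40 + 15 × 0.10 = 7.5. Under the alternatives simulated in Step 2, including 80/10%, the number is about 4 to 11. For 80% power at a hazard ratio of 0.5, Schoenfeld's formula gives 4(1.96 + 0.842)²/(ln 0.5)² = 4 × 7.849/0.4805 = 65.3, so 66 events. Freedman's gives (1.5/0.5)² × 7.849 = 70.6, so 71.

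**The case against.** The strongest case against has four parts.

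- **The plan does not say unstratified.** It says only log-rank tests. That stands: the exact criticism is that the stratum is not specified. It does not remove the point, because the default reading is the ordinary test, and silence leaves the choice open until after data are seen in an open-label study.
- **The loss of level needs balance within strata.** No blocks are described. That also stands. Balance within strata is the usual aim of stratifying, so it is a reasonable expectation, but it is not documented. Without it the level is near nominal and only a smaller power loss remains.
- **The effect is small unless risks differ greatly.** A reader might infer that the test runs at about half its nominal level. The documents do not support that as a general statement: they give no failure rates and do not say that the procedures differ in risk. It holds only under large assumed differences together with balance within strata.
- **Little depends on it.** The error is conservative, patency is secondary, and the stated purpose is to gather quality-of-life data for sizing a later trial. Accepted; this sets the priority.

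A reader might also infer that a stratified Cox hazard ratio and Kaplan-Meier curves within procedure are required. The plan promises no hazard ratio. With balanced allocation, a hazard ratio of 0.3 and the very unequal risks above, about 5 to 7.5 failures arise per trial, and in 10-27% of trials one arm has none, so no finite estimate exists. Curves by arm within procedure would rest on roughly 5 to 10 patients each.

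**Conclusion.** The point holds as a minor mismatch between design and analysis. The stratum used in randomisation is missing from the patency comparison. If allocation is balanced within strata and failure risk differs by procedure, the ordinary log-rank test is conservative and somewhat less powerful than the stratified one. The plausible cost runs from nothing (equal risks), through about 1 power point (20% v 40%), to about 4 to 7 points with a level near 2.5-3% (10-15% v 50-60%, hazard ratio 0.3). Part of that power gap is simply the unused level.

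All of these figures rest on assumed risks, hazard ratios and a two-sided 5% level. It would be wrong to conclude that the patency test is invalid or prone to false positives, or that stratifying would make it adequately powered. In the 50:50 scenarios of Step 2, including 80/10%, the stratified test reaches only about 9 to 20% power at a hazard ratio of 0.5.

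**What to change.** In the Analysis section, state that time to patency failure is compared between arms with a log-rank test stratified by the randomisation stratum (open or endovascular). It would help to state in Methods whether allocation is blocked within strata, since the size of the effect depends on it.

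The cost is one sentence of analysis wording. The stratum is already known from randomisation, and no patients, visits or data are added. With equal risks the result is essentially unchanged; without balance within strata the power loss is trivial at worst. A stratified Cox hazard ratio or Kaplan-Meier curves within procedure may be added, labelled as descriptive, with a note that the hazard ratio may not be estimable if one arm has no failures.
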